2.2 Analysis sets

Full Analysis Set

The Full Analysis Set (FAS) comprises all subjects that received any study drug. Subjects will be analyzed according to the treatment(s) received.

Safety Set

The Safety Set includes all subjects who received at least one dose of study treatment. Subjects will be analyzed according to the study treatment received, where treatment received is defined as the randomized/assigned treatment if the subject took at least one dose of that treatment or the first treatment received if the randomized/assigned treatment was never received.

Dose-Determining Set

The Dose-Determining Set (DDS) includes all subjects from the safety run-in and dose escalation part (Part 1) of the study who met the minimum exposure criterion and had sufficient safety evaluations, or experienced a dose-limiting toxicity (DLT) between C1D1 and C3D1. The minimum exposure required for combination treatments defined as follows:

- For ruxolitinib + rinaterkib study treatment arm, a subject has met the minimum exposure criterion if the subject takes at least 75% of the planned daily rinaterkib and ruxolitinib combination doses during the first two treatment cycles of dosing, i.e. at least 21 full dosing days out of the planned 28 days for the rinaterkib and ruxolitinib combination, and the subject takes at least 80% of the planned daily doses of ruxolitinib i.e. at least 23 full dosing days out of the planned 28 days for ruxolitinib.
- For all other study treatment arms, a subject has met the minimum exposure criterion if the subject takes all planned doses of the combination agent during the first two treatment cycles of dosing, and at least 80% of the planned daily doses of ruxolitinib i.e. at least 23 full dosing days (17 days for NIS793) out of the planned 28 days (21 days for NIS793) for ruxolitinib.

Subjects who do not experience a DLT between C1D1 and C3D1 are considered to have sufficient safety evaluations if they have been observed until C2D28, or C2D21 for the ruxolitinib + NIS793 study treatment arm, and are considered by both the sponsor and investigators to have enough safety data to conclude that a DLT did not occur.

Pharmacokinetic analysis set (PAS)

The Pharmacokinetic Analysis Set (PAS) includes all enrolled subjects who have an evaluable PK profile. A profile is considered evaluable if all of the following conditions are satisfied:

- Subject receives the planned treatments
- Subject takes the dose of study treatments

2.2.1 Subgroup of interest

The permanent enrollment halt led to limited data that are not sufficient for subgroup analysis. Subgroup analysis is not applicable for the primary and final analysis for this early terminated study.

2.3 Patient disposition, demographics and other baseline characteristics

The Full Analysis Set (FAS) will be used for all baseline and demographic summaries and listings unless otherwise specified. Summaries will be reported by treatment group (defined in Section 1-1) and for all subjects and listings will be reported by treatment group to assess baseline comparability. Subjects in Part 1 will be analyzed separately from the subject in Part 2. Data from Part 2 will be listed but not summarized.

Basic demographic and background data

All demographic and baseline disease characteristics data will be summarized and listed by treatment group. Categorical data (e.g. gender, age groups: <65 and \geq 65 years, race ethnicity, ECOG performance status etc.) will be summarized by frequency counts and percentages; the number and percentage of patients with missing data will be provided. Continuous data (e.g. age, weight, height etc.) will be summarized by descriptive statistics (N, mean, median, standard deviation, minimum and maximum).

Diagnosis and other baseline characteristics

Summary statistics will be tabulated for diagnosis and other baseline disease characteristics. This analysis will include the following: initial diagnosis of disease, most recent diagnosis of disease, time since initial diagnosis, time since most recent diagnosis, hemoglobin level (g/dL), absolute neutrophil count (ANC) (/ μ L), platelet count (/ μ L), spleen palpable (Yes/No), spleen length below left costal margin (cm), spleen volume (cm³), MFSAF Total Symptom Score, prior ruxolitinib duration (weeks).

Note: Prior ruxolitinib administration is recorded on Prior/Concomitant Medications eCRF pages.

Medical history

Medical history and ongoing conditions, including cancer-related conditions and symptoms entered on the (e) CRF will be summarized and listed by treatment group. Separate summaries will be presented for ongoing and historical medical conditions. The summaries will be presented by primary system organ class (SOC), preferred term (PT) and treatment arm. Medical history and current medical conditions will be coded using the Medical Dictionary for Regulatory Activities (MedDRA) terminology. The MedDRA version used for reporting will be specified in the CSR and as a footnote in the applicable tables/listings.

2.3.1 Patient disposition

Enrollment by country and center will be summarized for all screened patients and also by treatment group using the FAS.

The number (%) of treated patients included in the FAS will be presented overall and by treatment group. The number (%) of screened and not-treated patients and the reasons for screening failure will also be displayed. The number (%) of patients in the FAS who are still on treatment, who discontinued the study phases and the reason for discontinuation will be presented overall and by treatment group for core and extension treatment phase.

The following summaries will be provided: % based on the total number of FAS patients:

- Number (%) of patients who were treated (based on 'DAR' eCRF pages of each study treatment component completed with non-zero dose administered)
- Number (%) of patients who are still on-treatment (core) (based on the Disposition page and Subject Status page);

- Number (%) of patients who discontinued the core treatment phase (based on the Disposition page)
- Primary reason for study core treatment phase discontinuation (based on the Disposition page)
- Number (%) of patients who are still on-treatment (extension) (based on the Disposition page and Subject Status page);
- Number (%) of patients who discontinued the extension treatment phase (based on the Disposition page)
- Primary reason for study extension treatment phase discontinuation (based on the Disposition page)

Protocol deviations

The number (%) of patients in the FAS with any protocol deviation will be tabulated by deviation category (as specified in the study Data Quality Plan) overall and by treatment group for the FAS. All protocol deviations will be listed.

Summarize PDs that are not pandemic related and those that are, separately and in total.

For those related to the pandemic summarize “all COVID-19 pandemic related” together and by each specific relationship to COVID-19 if applicable/provided, following the COVID-19 (Coronavirus) Guidance for Clinical Trial Teams and Trial Monitoring Associates-*Protocol Deviations and Data Collection: Go Live after 01-Dec-2020 Relationship to COVID-19 via CRFs Version 2.0*. Percentage is out of total patients in the FAS.

Analysis sets

The number (%) of patients in each analysis set (defined in [Section 2.2](#)) will be summarized by treatment group.

2.4 Treatments (study treatment, rescue medication, concomitant therapies, compliance)

2.4.1 Study treatment / compliance

Duration of exposure, actual cumulative dose, dose intensity (DI) and relative dose intensity (RDI) will be summarized by treatment group, separately for each component of study treatment (Ruxolitinib and appropriate novel agent). The duration of exposure to study treatment will also be presented for each treatment group. Duration of exposure will be categorized into time intervals; frequency counts and percentages will be presented for the number (%) of subjects in each interval. The number (%) of subjects who have a dose change, and the reasons, will be summarized by treatment group. Data in this section is based on the study treatment CRF pages.

Subject level listings of all doses administered on treatment along with dose change reasons will be produced.

The Safety Set will be used for all summaries and listings of study treatment.

Duration of exposure to study treatment

Duration of exposure to study treatment is calculated by taking into account the duration of exposure to ruxolitinib and/or any novel agent partner for each treatment group:

Duration of exposure to study treatment (days) for each treatment group = (last date of exposure to study treatment) – (date of first administration of study treatment) + 1.

The first date of exposure to study treatment for each treatment group is the earliest of the first dates of exposure to ruxolitinib or any novel agent partner.

The last date of exposure to study treatment for each treatment group is the latest of the last dates of exposure to ruxolitinib or any novel agent partner (see Table 2-5).

Summary of duration of exposure of study treatment in appropriate time units will include categorical summaries and continuous summaries (i.e. mean, standard deviation etc.) using appropriate units of time.

Duration of exposure to investigational drug (ruxolitinib or any novel agent partner)

Duration of exposure to investigational drug (days) = (last date of exposure to investigational drug) – (date of first administration of investigational drug) + 1.

Table 2-5 Definition of last date of exposure of study drug

Scenario	Definition of last date of exposure of study drug	Example
Ruxolitinib (INC424) Rineterkib (LTT462)	Date of last administration of a non - zero dose of the study drug.	Example 1: A patient had a permanent discontinuation of the study drug on 06Jan2013 after being put on a temporary interruption since 01Jan2013. In this case the last date of exposure is 31Dec2012.
Siremadlin (HDM201) Crizanlizumab (SEG101) Sabatolimab (MBG453) NIS793	The planned end date of the last cycle in which the last non-zero dose of the investigational drug was last administered. Note: If the patient died or was lost to follow-up before the derived last date, the last date of exposure to investigational drug is the date of death or the date of last contact, respectively. If the derived last date of exposure goes beyond the data cut-off date, it should be truncated to the date of data cut-off.	Example 2: Siremadlin is in a 28-day cycle with once a day administration for Day 1-5 of each cycle. The last date of exposure is the date of administration in the last cycle + 23 days. Example 3: Crizanlizumab is in a 28-day cycle with one iv infusion in the beginning of the cycle and with a 2 nd loading dose after 14 days of initial dosing for Cycle1 only. The late dose of exposure is the date of last infusion in Cycle 1 + 13 days if Cycle 1 is the last cycle.

		
The last date of exposure is the date of first infusion in the last cycle + 27 days if the last cycle is post Cycle 1.
 
Example 4: Sabatolimab is in a 28-day cycle with one iv infusion in the beginning of the cycle. The last date of exposure is the date of first infusion in the last cycle + 27 days
 
Example 5: NIS793 is in a 21-day cycle with one iv infusion in the beginning of the cycle. The last date of exposure is the date of first infusion in the last cycle + 20 days

--	--	--

Summary of duration of exposure of an investigational drug will include categorical summaries based on 12 weeks intervals and using descriptive statistics (mean, standard deviation etc). The duration includes the periods of temporary interruption.

Cumulative dose

Cumulative dose of a study treatment is defined as the total dose given during the study treatment exposure and will be summarized for each of the study treatment components. The **actual cumulative dose** refers to the total actual dose administered, over the duration for which the subject is on the study treatment as documented in the Dose Administration eCRF.

For subjects who did not take any drug the cumulative dose is by definition equal to zero.

The **planned cumulative dose** for a study treatment component is the total planned dose as per the protocol up to the last date of investigational drug administration. The planned cumulative dose will not be summarized/listed. It will be used for relative dose intensity calculations.

For each component of study treatment which is administered daily the planned cumulative dose is the planned starting dose summed over the duration of exposure for the component. For each component of study treatment that has cyclic administration, the planned cumulative dose is the sum of planned total starting dose in a cycle times the number of complete cycles the patient should have been over the duration exposure, plus the total dose expected in the last incomplete cycle.

Dose intensity and relative dose intensity

Dose intensity (DI) for subjects with non-zero duration of exposure is defined as follows:

For Ruxolitinib and Rineterkib:

DI (mg/day) = Actual Cumulative dose (mg) / Duration of exposure to study drug (in days).

For Siremadlin, sabatolimab and NIS793:

DI (mg/week) = Actual Cumulative dose (mg) / Duration of exposure to study drug (in weeks).

Example 1, the duration of exposure to sitemedlin is 24 weeks (6 cycles) and the subject receives 20 mg sitemedlin daily i.v. infusion on Days 1 to 5 of each cycle:

DI (mg/week) = Actual Cumulative dose (mg) / Duration of exposure to study drug (in weeks)
= $20*5*6$ (mg) / 24 (weeks) = 25 (mg/week).

Example 2, the duration of exposure to simelestat is 24 weeks (6 cycles) and the subject receives 800 mg simelestat i.v. infusion on Day 1 of each cycle:

DI (mg/week) = Actual Cumulative dose (mg) / Duration of exposure to study drug (in weeks)
= $800*6$ (mg) / 24 (weeks) = 200 (mg/week).

Example 3, the duration of exposure to NIS793 is 24 weeks (8 cycles) and the subject receives 2100 mg NIS793 i.v. infusion on Day 1 of each cycle:

DI (mg/week) = Actual Cumulative dose (mg) / Duration of exposure to study drug (in weeks)
= $2100*8$ (mg) / 24 (weeks) = 700 (mg/week).

For Crizanlizumab:

DI (mg/kg/week) = Actual Cumulative dose (mg/kg) / Duration of exposure to study drug (in weeks).

For example, the duration of exposure to crizanlizumab is 24 weeks (6 cycles) and the subject receives 5 mg/kg crizanlizumab IV infusion every 4 weeks with a second loading dose after 14 days of the initial dose (7 IV infusion of crizanlizumab at 5 mg/kg):

DI (mg/kg/week) = Actual Cumulative dose (mg/kg) / Duration of exposure to study drug (in weeks)
= $5*7$ (mg/kg) / 24 (weeks) = 1.46 mg/kg/week.

For subjects who did not take any drug the DI is by definition equal to zero.

Planned dose intensity (PDI) is defined as follows:

For Ruxolitinib and Rinaterkib:

PDI (mg/day) = Planned Cumulative dose (mg) / Duration of exposure (in days).

For Sitemedlin, Simelestat and NIS793:

DI (mg/week) = Planned Cumulative dose (mg) / Duration of exposure (in weeks).

For Crizanlizumab:

DI (mg/kg/week) = Planned Cumulative dose (mg/kg) / Duration of exposure (in weeks).

Relative dose intensity (RDI) is defined as follows:

For Ruxolitinib and Rinaterkib:

RDI = DI (mg/day) / PDI (mg/day).

For Sitemedlin, Simelestat and NIS793:

RDI = DI (mg/week) / PDI (mg/week).

For Crizanlizumab:

RDI = DI (mg/kg/week) / PDI (mg/kg/week).

DI and RDI will be summarized separately for each of the study treatment components (ruxolitinib and novel agent combination) using the duration of exposure of each of the components.

Dose changes, interruptions or permanent discontinuations

The number of subjects who have dose changes, permanent discontinuations or interruptions, and the reasons, will be summarized separately for each of the study treatment components.

‘Dose changed’, ‘Dose interrupted’, and ‘Dose permanently discontinued’ fields from the Dosage Administration CRF pages (DAR) will be used to determine the dose change, dose interruptions, and permanent discontinuations, respectively.

The corresponding fields ‘Reason for dose change/dose interrupted’ and ‘Reason for permanent discontinuation’ will be used to summarize the reasons.

A dose change is either ‘change in prescribed dose level’ or ‘dosing error’ where actual dose administered/total daily dose is different from the prescribed dose.

Dose interruptions are captured in the eCRF following the Oncology Data standard Reference manual and CRF Completions Guidelines. Depending on the dosing administration schedule (e.g. continuous dosing, interval dosing), data would be collected in different fashion. For instance, for continuous dosing an interruption is defined as a dose of zero in a unit of time between two non-zero dosing records. In general any rest period as part of the regimen/schedule is not considered as an interruption.

For the purpose of summarizing interruptions and reasons, in case multiple entries for interruption that are entered on consecutive days with different reasons will be counted as separate interruptions. However, if the reason is the same in this block of entries, then it will be counted as one interruption.

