6.7.2.3 Crizanlizumab

Crizanlizumab (SEG101) will be administered at 5 mg/kg Q4W on Day 1 of every 28-day cycle with an additional loading dose administered at Cycle 1 Day 15 via IV infusion over 30 minutes (up to 2 hours, if clinically indicated) as described in the pharmacy manual starting approximately within the next hour after ruxolitinib administration, if and when administered. There should be a period of at least 1 hour after the infusion whereby the subject requires close observation.

Sabatolimab (MBG453) will be administered at 800 mg dose level Q4W on Day 1 of every 28-day cycle via IV infusion over 30 minutes (up to 2 hours, if clinically indicated) as described in the pharmacy manual starting approximately within the next hour after ruxolitinib administration, if and when administered. There should be a period of at least 1 hour after the infusion whereby the subject requires close observation.

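### The SAP's planned-dose formula for cyclic drugs, read literally, has no term for crizanlizumab's Cycle 1 Day 15 loading dose and so conflicts with the SAP's own general definition; a compliant six-cycle subject would show a relative dose intensity of 117% instead of 100%

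*SAP*

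**What the plan says.** SAP Section 2.4.1, under Cumulative dose, makes two statements about planned cumulative dose.

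- The general definition: planned cumulative dose "is the total planned dose as per the protocol up to the last date of investigational drug administration".
- The computing rule for cyclic drugs: "the planned cumulative dose is the sum of planned total starting dose in a cycle times the number of complete cycles" that the patient should have had over the exposure period, "plus the total dose expected in the last incomplete cycle".

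The quantity is not summarized or listed. Of its purpose the SAP says: "It will be used for relative dose intensity calculations".

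On the crizanlizumab schedule, Protocol Section 6.7.2.3 gives 5 mg/kg on Day 1 of each 28-day cycle, "with an additional loading dose administered at Cycle 1 Day 15 via IV infusion over 30 minutes". SAP Table 2-5 agrees: "with a 2 nd loading dose after 14 days of initial dosing for Cycle1 only". The dose-intensity example in Section 2.4.1 covers 24 weeks (six cycles) and counts the extra infusion: "with a second loading dose after 14 days of the initial dose (7 IV infusion of crizanlizumab at 5 mg/kg". It arrives at 1.46 mg/kg/week. The SAP gives no planned dose, planned dose intensity (PDI) or RDI figure for crizanlizumab.

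**The concern.** Multiplying a single per-cycle dose by the number of cycles works only when every cycle plans the same dose. Crizanlizumab plans 10 mg/kg in Cycle 1 and 5 mg/kg in each later cycle. The numerator of RDI counts the loading dose, as the dose-intensity example shows, while the rule for the denominator has no place for it.

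If the programming follows the cyclic sentence as written, compliant subjects in this arm appear to have received more than planned, and a subject who missed the loading dose appears fully dosed. Because planned cumulative dose is never displayed, a reader of the exposure table would see only the resulting RDI and could not tell which denominator produced it.

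**Working it through.** **Inputs**

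| Quantity | Value | Source |
|---|---|---|
| Dose per infusion | 5 mg/kg | Protocol 6.7.2.3 |
| Scheduled infusions, six cycles | Days 1, 15, 29, 57, 85, 113, 141: 7 in all | Protocol 6.7.2.3; SAP 2.4.1 example |
| Last exposure date after Cycle 1 | first infusion of the last cycle + 27 days | SAP Table 2-5 |
| DI and PDI | actual or planned cumulative dose divided by weeks of exposure | SAP 2.4.1 |
| RDI | DI / PDI | SAP 2.4.1 |

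**1. Reproduce the SAP's figure.** DI = 5 × 7 / 24 = 35 / 24 = 1.458, which rounds to the stated 1.46 mg/kg/week.

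**2. Count complete cycles.** Cycle 6 Day 1 is Day 1 + 28 × 5 = 141. Exposure ends on Day 141 + 27 = 168, which is 24.0 weeks or exactly six cycles. No cycle is incomplete, so the incomplete-cycle term adds nothing and cannot supply the missing infusion.

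**3. Simplify RDI.** The weeks of exposure cancel, so RDI = actual cumulative dose / planned cumulative dose.

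**4. Compliant subject, six cycles, actual dose 35 mg/kg**

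| Rule for planned dose | Planned (mg/kg) | PDI (mg/kg/week) | RDI |
|---|---|---|---|
| Cyclic sentence, 5 mg/kg per cycle | 5 × 6 = 30 | 30/24 = 1.25 | 35/30 = 116.7% |
| General definition, protocol schedule | 10 + 5 × 5 = 35 | 35/24 = 1.458 | 35/35 = 100% |

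**5. Other durations.** For k complete cycles the compliant subject receives 5(k + 1) and the cyclic sentence plans 5k, so RDI = (k + 1)/k: 200% after one cycle, 150% after two, 108.3% after twelve. The distortion is largest for subjects who stop early.

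**6. Missed loading dose, other six infusions given.** Actual dose is 30 mg/kg. The cyclic sentence gives 30/30 = 100%; the protocol schedule gives 30/35 = 85.7%.

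**7. Other cyclic drugs, using the SAP's own examples.** Siremadlin is 20 × 5 × 6 = 600 mg both planned and received, sabatolimab 800 × 6 = 4,800 mg, NIS793 2,100 × 8 = 16,800 mg. Each plans a constant dose per cycle, so RDI is 100% for a compliant subject. Only crizanlizumab is affected.

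**The case against.** The strongest reply is that the section already contains the right answer. The general definition refers to the total dose planned by the protocol, the protocol schedules the Day 15 infusion, and the result is 35 mg/kg and 100%. The opening words of the cyclic sentence could also be taken as a sum over unequal cycles, 10 + 5 × 5 = 35. The SAP plainly knows that Cycle 1 differs, since Table 2-5 gives it a separate last-exposure rule and the dose-intensity example counts seven infusions. No printed figure is wrong.

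Much of this stands. It makes the matter a conflict between two statements in one section, and a programmer who starts from the general definition would get the correct value. It does not remove the conflict. The cyclic sentence is the only computing rule given for these drugs, it is phrased as a multiplication, and no planned-dose example settles how Cycle 1 is handled.

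Three stronger readings are tempting, and the documents do not support them.

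- A reader might apply the Cycle 1 total of 10 mg/kg to every cycle and obtain 35/60 = 58%. That plans a loading dose in each cycle, which Table 2-5 rules out. In the neighbouring sentence on daily drugs, the starting dose most naturally means the dose initially assigned.
- A reader might conclude that a missed loading dose would go unnoticed. RDI alone would not show it, but Section 2.4.1 also plans subject-level listings of administered doses and summaries of actual cumulative dose. The Dose-Determining Set criterion for this arm (SAP Section 2.2) requires every planned dose of the combination agent in the first two cycles.
- A reader might treat RDI as the tolerability measure for the arm. The Part 1 primary endpoint is dose-limiting toxicity; RDI is one of several descriptive exposure summaries.

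**Conclusion.** The cyclic-drug rule in SAP Section 2.4.1 is wrong as written for crizanlizumab and conflicts with the general definition beside it. Followed literally at 5 mg/kg per cycle, it gives a compliant six-cycle subject an RDI of 117% instead of 100%, and a subject who missed only the loading dose 100% instead of 86%.

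These figures assume complete cycles, no dose change, and a programmer who applies the cyclic sentence literally. The SAP prints no RDI for this drug, so a reader should not infer that a wrong value has been reported; the documents do not show which denominator was used.

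The consequence is small. It affects one descriptive summary in an arm planned at about 6 subjects (Protocol Section 3), and no endpoint, threshold or dose decision uses it. With so few subjects, though, a few distorted values would shift the summary, and the table itself would not reveal the cause.

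**What to change.** Add one sentence to SAP Section 2.4.1: for crizanlizumab, planned cumulative dose is the sum of all protocol-scheduled infusions falling within the derived duration of exposure in Table 2-5, including Cycle 1 Day 15 when it falls within that period. Tying the rule to derived exposure settles early stops. A subject who receives only the Day 1 infusion has exposure ending on Day 1 + 13 = Day 14, so the planned dose is 5 mg/kg. A subject who receives both Cycle 1 infusions and then stops has exposure to Day 15 + 13 = Day 28, so the planned dose is 10 mg/kg.

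Next to the existing dose-intensity example, add its planned counterpart: PDI = 35/24 = 1.46 mg/kg/week and RDI = 35/35 = 100%.

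The cost is one sentence, one example and about one line of programming. Nothing in the treatment schedule or data collection changes. If the exposure tables are already programmed, check which denominator was used and rerun the crizanlizumab RDI summary if it was the flat per-cycle dose.

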Every effort must be made to follow the schedule of assessments within the windows outlined in the protocol.

Study visits with scheduled PK sampling should be scheduled in the morning so that a pre-dose PK blood sample can be collected.

The preferred sequence for assessments during study visits is ECG collection first, followed by vital signs, and blood sampling.

For Japan only, subjects enrolled in the crizanlizumab arm of Part 1 (Arm 2) are required to be hospitalized in the first 7 days of study treatment.

As per Section 4.6, during a Public Health emergency as declared by Local or Regional authorities i.e. pandemic, epidemic or natural disaster that limits or prevents on-site study visits, alternative methods of providing continuing care may be implemented by the investigator as the situation dictates. If allowed by local Health Authority and depending on operational capabilities, phone calls, virtual contacts (e.g. tele consult) or visits by site staff/ home nursing staff to the participant's home, can replace on-site study visits, for the duration of the disruption until it is safe for the participant to visit the site again.

Table 8-1 Allowable visit windows

Visit name	Assessments	Window allowed
Screening	MRI/CT scan of abdomen (all parts)	within 8 weeks prior to first dose of study treatment
	Cardiac imaging (MUGA or echocardiogram or cardiac MRI) and ophthalmologic exams (Part1 only)	≤ 28 days before C1D1
	Bone marrow biopsy (part 2 and 3)	within 8 weeks prior to first dose of study treatment
	All other assessments	≤ 28 days before C1D1
C1D1	IRT dispensing call	-3 days
(Core Phase)	Cardiac imaging (MUGA or echocardiogram or cardiac MRI) and ophthalmologic exams (Part 2 and Part 3)	-3 days
	All other visit assessments and administration of study drugs	NA
Day 1 visit of all subsequent cycles	Cardiac imaging and ophthalmologic exams	-7 days
(Core and extension)	All other visit assessments and administration of study drugs	± 3 days
During Treatment and Safety Follow-up periods	PK sampling	Refer to PK sample tables in Section 8.5.2
EOT Core Phase for subjects not entering in extension;	All assessments	+ 7 days after last dose of study treatment (except for MRI/CT scan or bone marrow biopsy if completed in
EOT extension		the past 12 weeks)
EOT core for subjects entering in extension	All assessments	± 3 days (EOT core and C1D1 extension visits
and C1 D1 (extension)		must be performed on the same day)

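### SAP 2.4.1 gives two planned-dose rules for cyclic drugs that disagree when the last cycle starts late, and one of them charges a dose that was never due

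*SAP*

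**What the plan says.** The paragraph on cumulative dose in SAP 2.4.1 defines the planned amount twice.

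- **General sentence.** Planned cumulative dose "is the total planned dose as per the protocol up to the last date of investigational drug administration".
- **Cyclic sentence.** For drugs given in cycles, the planned starting dose per cycle is multiplied by "the number of complete cycles the patient should have been over the duration exposure, plus the total dose expected in the last incomplete cycle".

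The duration used by the cyclic sentence comes from Table 2-5. For siremadlin, crizanlizumab, sabatolimab and NIS793 the last exposure date is "The planned end date of the last cycle in which the last non-zero dose of the investigational drug was last administered". The worked examples count from the actual administration. For sabatolimab, "The last date of exposure is the date of first infusion in the last cycle + 27 days"; for NIS793, "The last date of exposure is the date of first infusion in the last cycle + 20 days"; for siremadlin, "The last date of exposure is the date of administration in the last cycle + 23 days". The text after the table adds: "The duration includes the periods of temporary interruption".

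RDI is dose intensity divided by planned dose intensity. The planned cumulative dose is used for RDI but is not itself tabulated or listed.

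In Protocol Section 8, Table 8-1, the row "All other visit assessments and administration of study drugs" for Day 1 of later cycles allows 3 days either side. The same section advises against siremadlin cycles shorter than 28 days.

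**The concern.** Within a cycle, all doses fall at the start: Day 1 for sabatolimab and NIS793, Days 1 to 5 for siremadlin. If the last cycle starts a day late, exposure is n full cycles plus one day. That odd day looks like Day 1 of another cycle, so the cyclic sentence adds a dose to the denominator although the subject missed nothing.

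Two programmers could therefore report different RDIs for the same subject, each following the SAP. Under the cyclic sentence, a sabatolimab subject with all 6 infusions, the last one a day late, shows 85.7%. A subject who skipped one of 6 infusions and finished on schedule shows 5/6 = 83.3%. The table would hardly separate a one-day slip from a missed cycle. With about 6 subjects planned per safety run-in arm, one or two such values would shift the arm's summary. Because the planned dose is not shown, a reader could not see the cause.

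**Working it through.** **The plan's own figures.** Dose intensity is actual dose divided by weeks of exposure.

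- Siremadlin: 20 × 5 × 6 / 24 = 25 mg/week
- Sabatolimab: 800 × 6 / 24 = 200 mg/week
- NIS793: 2100 × 8 / 24 = 700 mg/week
- Crizanlizumab: 5 × 7 / 24 = 1.46 mg/kg/week

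All four match the SAP. Each uses whole cycles, and the SAP gives no worked RDI, so no example tests a late last cycle.

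**Formula.** Dose intensity and planned dose intensity share the same duration, so RDI = actual dose / planned dose. With cycle length L, n fully dosed cycles and a last cycle d days late, duration = nL + d. The cyclic sentence gives n cycles of dose plus whatever falls in the first d days of a cycle.

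**One case in full.** Sabatolimab, 6 infusions, the last on Day 142 instead of Day 141. Last exposure is Day 142 + 27 = Day 169, and 169 = 6 × 28 + 1. The planned dose is 6 × 800 + 800 = 5600 mg against 4800 mg given, so RDI = 85.7%. Under the general sentence, six infusions fall due by Day 142 (Days 1, 29, 57, 85, 113 and 141). The planned dose is then 4800 mg and RDI is 100%.

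**All cyclic drugs, every dose given.** Siremadlin is counted dose by dose, and the crizanlizumab loading dose is counted as planned.

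| Drug, cycles | Days late | Actual | Planned (cyclic) | RDI (cyclic) | RDI (general) |
|---|---|---|---|---|---|
| Sabatolimab, 6 | 1–3 | 4800 mg | 5600 mg | 85.7% | 100% |
| Sabatolimab, 2 | 1–3 | 1600 mg | 2400 mg | 66.7% | 100% |
| NIS793, 8 | 1–3 | 16,800 mg | 18,900 mg | 88.9% | 100% |
| Crizanlizumab, 6 | 1–3 | 35 mg/kg | 40 mg/kg | 87.5% | 100% |
| Siremadlin 20 mg, 6 | 1 | 600 mg | 620 mg | 96.8% | 100% |
| Siremadlin 20 mg, 6 | 3 | 600 mg | 660 mg | 90.9% | 100% |
| Siremadlin 20 mg, 6 | 5 or more | 600 mg | 700 mg | 85.7% | 100% |

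**Early last cycle.** With the sixth sabatolimab infusion one day early, duration is 167 days = 5 × 28 + 27. The cyclic sentence gives 5 + 1 = 6 planned infusions and RDI 100%, so its error runs only downward. The general sentence, applied by calendar day, counts only 5 infusions due by Day 140 and gives 6/5 = 120%. Neither sentence is sound as it stands.

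**Effect on dose intensity.** In the Day 142 case it is 4800 / (169/7) = 198.8 mg/week, close to 200. The planned dose intensity is 5600 / (169/7) = 232 mg/week, so the distortion is entirely in the planned term.

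**The case against.** The strongest reply is that the cyclic sentence need not be read this way. It refers to cycles the patient should have been in, and its last incomplete cycle could mean a cycle that was started and then cut short by death, loss to follow-up or data cut-off, the cases in the Table 2-5 note. On that reading no extra cycle arises and RDI is 100%, in line with the general sentence. This is a fair reading, and it stands to this extent: the SAP has an ambiguity, not a settled rule. It does not remove the problem, because the sentence ties the count to the duration of exposure, which includes delays, and nothing limits the term to truncated cycles.

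The second reply concerns impact, and it also stands. RDI enters no DLT analysis, dose decision or efficacy result. The Dose-Determining Set has its own minimum-exposure rule. SAP 2.4.1 also reports actual cumulative dose, dose intensity, duration and dose changes with reasons, and lists every dose.

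A reader might infer more than the documents support:

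- That fully dosed subjects will be reported at about 67–91%. This assumes the literal reading. The 67% end also needs only two cycles, and for siremadlin a delay of 5 or more days, outside the window, if doses are counted singly.
- That one late day costs siremadlin a whole cycle. It costs one of five doses, unless the incomplete cycle is charged in full.
- That the right values are 95–99%. Those come from prorating by time, a method neither document uses. The SAP's other definition gives 100%.

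**Conclusion.** The two definitions conflict whenever the last cycle of a cyclic drug starts late, and they need to be reconciled. Read literally, the cyclic sentence lowers RDI to n/(n+1) for sabatolimab and NIS793. It has the same kind of effect on crizanlizumab. For siremadlin it adds one of five cycle doses to the planned total per late day, up to five. At the planned core duration a fully dosed subject with an in-window late last cycle would show 85.7% (sabatolimab), 88.9% (NIS793), 87.5% (crizanlizumab) or 90.9–96.8% (siremadlin), against 100% under the general sentence.

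These figures assume full dosing, lateness measured from the Cycle 1 Day 1 calendar, and no truncation. How many subjects had a late last cycle is not in the documents, so the effect on arm summaries cannot be stated. Ruxolitinib and rineterkib use the daily rule and do not have this artefact. It is worth correcting because reported values could be wrong and the repair is cheap, but no conclusion about safety or dose depends on it.

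**What to change.** Replace the cyclic sentence with one rule. Planned cumulative dose = planned starting dose per cycle × number of protocol cycles from the first through the last dosed cycle, counting any cycle skipped in between, plus the Cycle 1 Day 15 loading dose for crizanlizumab where due. State that no dose is charged for days after the last dosed cycle that arise only because that cycle started late. State also how a last dosed cycle cut short by death, loss to follow-up or data cut-off is counted. Align the general sentence, and add a worked example with a late last cycle.

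Under this rule each fully dosed case in the table gives 100%, an early last infusion also gives 100%, and a skipped sabatolimab infusion among six cycles still gives 4000/4800 = 83.3%. Short delays remain visible in dose intensity.

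Do not prorate the planned dose by time. For the SAP's own compliant crizanlizumab example, proration plans 5 × 168/28 = 30 mg/kg against 35 given, an RDI of 116.7%. If Cycle 1 is the last cycle and both infusions were given, it plans 5 mg/kg against 10, or 200%. A second 28-day-cycle infusion given 3 days early yields 56/53 = 105.7%.

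The cost is a sentence or two of SAP text, one example and a small programming change, with no new data. If RDI tables have already been run for the primary CSR, check which sentence was programmed.
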